5.3 Description of Proposed Study Intervention

Our proposed intervention will be constructed within the aforementioned theoretical framework, using existing literature to incorporate strategies to reduce modifiable barriers to endocrine therapy initiation. [name] developed the intervention outline with expertise from co-investigators Drs. [name] and [name] who are experts in cancer outcomes research and breast oncology and health equity, respectively. The data gathered from the semi-structured interviews has informed the intervention and be instrumental in refining it to optimize patient-centeredness.

The nurse-led intervention will be a brief, two-session, culturally competent, evidence-based intervention via videoconferencing software administered by a breast oncology nurse practitioner. The sessions will begin once baseline assessments and enrollment are complete, and the sessions will be approximately 2 weeks apart. Both sessions will aim to take place prior to the planned and agreed upon AET start date per the treatment plan with their oncology team. Study staff will work with patients on a case-by-case basis to schedule the sessions in a timeline that aligns with their treatment plan. Patients have the option to request attending these sessions via phone or in person.

The intervention and study materials will be translated into Spanish and delivered by nurse practitioner, [name], in either English or Spanish. An interpreter will be present either in person or remotely for the intervention for patients who speak Spanish only. Both sessions will take place within one month of the baseline assessment. The intervention will target known modifiable barriers to AET initiation, including support and communication with clinicians, perceived therapeutic efficacy of AET, and managing expectations of symptoms and side effects, but will be primarily driven by barriers identified by the patient. Therefore, the session will begin by probing and identifying the individual and culture-specific barriers to initiation in multiple domains. The interventionist and patient will then problem-solve barriers to initiation through motivational interviewing, cognitive-behavioral techniques, and medication education. The intervention is informed by the Health Belief Model (HBM), the Cognitive Model of Adjustment to Cancer, and Motivational Interviewing Techniques. First, the intervention will address perceived risk and medication efficacy in line with the HBM, which maintains that the health behavior (i.e., initiating AET) will be adopted if the patient perceives (a) risk for a condition, (b) that the medication will reduce risk, (c) that benefits outweigh costs, and (d) self-efficacy for taking medication. Second, driven by the Cognitive Model of Adjustment to Cancer, the intervention will include strategies for enhancing coping with side effects, reframing cognitive self-talk about AET efficacy, and identifying and enhancing social support. CBT is effective in helping patients manage concerns, fears, and actual cancer-related side effects. Finally, Motivational Interviewing techniques will help the patient explore and resolve ambivalence with attention to their readiness for change. Sessions will be audio-recorded and at least 10% will be reviewed for treatment fidelity. Intervention acceptability will be evaluated using the CSQ.

5.4 Data Collection and Provisions to Protect the Privacy Interests of Subjects

Participants will be given the option to complete the above instruments either on paper, over a secure REDCap portal or over the telephone. Study staff will send assessments to participants at the start of their timepoint window and will follow-up periodically throughout to ensure receipt and completion of assessments. Assessments that are completed on paper will be entered into the secure REDCap database by study staff.

Patients will receive an Intervention Manual which has been informed by the Qualitative Phase of this study (21-331) (Appendix 9.25).

Patients will additionally receive a copy of the Intervention Manual and a welcome letter with study expectations (Appendix 9.21, 9.22), and a study timeline document (Appendix 9.23, 9.24). As detailed in the Data Safety Monitoring Plan (Section 6.0), all subjects will receive a confidential number identifier. All participants will be identified on study assessments by their number identifier.

Identifiers, such as name, will only be used during the initial data retrieval process and can be destroyed once all data records have been obtained and data analysis has been completed as discussed previously.

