5.0 Study Design and Methods

5.1 Design/Study Type

The present protocol proposes to examine the single-arm pilot trial to examine feasibility and acceptability of a patient-centered, evidence-based, culturally competent, tailored intervention to encourage breast cancer survivors who have not begun taking adjuvant endocrine therapy to initiate the medication, enriching for Black, Hispanic/Latina, and Asian American BCS. AET initiation will be measured by a self-report questionnaire. Participants will complete assessments at baseline (within 14 days of consent), 1-month, and 3-months post-baseline measuring beliefs about AET necessity, satisfaction with patient-physician communication, perceived social support and quality of life.

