5.2 Selection of Instruments

Instrument/Measure	Screening	Baseline (14-day window)	1-month follow-up (+/- 7 day)	3-month follow-up (+/- 7 day)
Chart Review	X			
Screening Questions (AET initiation)	X			
Demographics		X		
AET Initiation Question		X	X	X
Functional Assessment of Chronic Illness Therapy- Treatment Satisfaction-Patient Satisfaction (FACIT-TS-PS)		X	X	X
Beliefs about Medicines Questionnaire – Adjuvant Endocrine Therapy (BMQ-AET)		X	X	X
Multidimensional Scale of Perceived Social Support (MSPSS)		X	X	X
Functional Assessment of Cancer Therapy-Breast (FACT-B)		X	X	X
Hospital Anxiety and Depression Scale (HADS)		X	X	X
Self-Efficacy for Managing Symptoms Questionnaire (Self-Efficacy for Symptoms)		X	X	X
Measure of Current Status – Part A (MOCS)		X	X	X
Client Satisfaction Questionnaire (CSQ)			X	

Screening:

EHR Factors: The following information will be collected from participant EHR: MGH Main vs Affiliate site vs DFCI sites, demographic information, breast cancer stage, treatment (e.g., surgery, chemotherapy, radiation), AET type, approximate recommended AET start date, and medical or psychological co-morbidities.

AET Initiation questions: A question will be administered asking patients whether they have started taking their daily AET (yes vs. no). Patients who have not yet started AET will be considered eligible for study participation. Patients will also be asked how hesitant they are about starting their recommended hormonal therapy medication on a scale of 0-10.

Outcome Measures:

Demographics Questionnaire: Participants will self-report their age, gender, race/ethnicity, marital status, education level, and relationship status.

AET Initiation Question: This one item instrument will ask patients: At different times throughout your participation in this study, you may or may not be taking/have started taking your hormonal therapy. “At this time, are you currently taking your hormonal therapy (e.g., Tamoxifen, Anastrozole/Arimidex, Exemestane/Aromasin, Letrozole/Femara)?” Patients will self-report their initiation of endocrine therapy.

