Client Satisfaction Questionnaire (CSQ):⁴² The CSQ is a 3-item, validated measure to assess satisfaction with services provided to the patient, and asks questions such as, "to what extent has our program met your needs?" Each item is answered on a scale of 1-4. This will be administered at the 1-month assessment to evaluate intervention participants only to examine intervention acceptability. The total score range is 3-12.

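### The 1-month packet, with the only CSQ, is sent from about day 23, but session 2 may fall as late as about day 30, so some acceptability ratings can precede the end of the program

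*Combined protocol and SAP*

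**What the plan says.** **Assessment timing.** Section 5.1 anchors the follow-ups to baseline: "Participants will complete assessments at baseline (within 14 days of consent), 1-month, and 3-months post-baseline". The schedule table in Section 5.2 gives the window as "1-month follow-up (+/- 7 day". Section 5.4 states when the packet goes out: "Study staff will send assessments to participants at the start of their timepoint window". Staff then follow up through the window until it is completed.

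**Session timing.** Section 5.3 says "The sessions will begin once baseline assessments and enrollment are complete", that "the sessions will be approximately 2 weeks apart", and that "Both sessions will take place within one month of the baseline assessment". No day is fixed for session 1: "Study staff will work with patients on a case-by-case basis to schedule the sessions in a timeline that aligns with their treatment plan".

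**What the 1-month packet carries.** It holds the CSQ, of which Section 5.2 says: "This will be administered at the 1-month assessment to evaluate intervention participants only to examine intervention acceptability". The schedule table shows no CSQ at 3 months. Sections 7.1 and 7.5 make satisfaction above the CSQ midpoint in more than 75% of participants one of the four feasibility and acceptability criteria. Section 7.5 also uses the one-month data for the AET initiation rate and for the paired t-tests from baseline.

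**The concern.** The assessment runs on a clock that starts at baseline and opens a week before the one-month mark. The sessions run on a looser clock that closes at the one-month mark. Nothing links the two. A woman seen on days 12 and 26 is fully on schedule, yet she is sent the CSQ and every one-month scale on day 23, after one session of two.

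The CSQ is the most exposed measure. It asks how well the program met her needs, it is the only quantitative measure behind the acceptability criterion, and it is not repeated, so a rating given too early cannot be recovered. In a pilot of up to 35 women, a few such ratings can matter to a threshold of 75%. The one-month paired comparisons are exposed in the same way, because they could pool mid-intervention scores with post-intervention scores.

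**Working it through.** **Is there a stated figure to reproduce?** The protocol gives no day numbers for the window. Its only calculation for a one-month outcome is the maximum width of the exact 95% interval for AET initiation with 30 participants, 37.4% (Section 7.5). The Clopper-Pearson interval is widest at 15 of 30, with width 37.41%, so that figure is confirmed. The timing point does not depend on it.

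**Inputs.** M = length of one month in days (not stated; 30 assumed, 28 to 31 as the range). Window half-width = 7 days (Section 5.2). Packet sent at window opening (Section 5.4). Latest session 2 = day M (Section 5.3). Gap between sessions = 14 days (Section 5.3, where it is approximate).

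**Formulas.**
- Packet sent: M − 7
- Window closes: M + 7
- Latest session 1: M − 14
- Last session 1 with session 2 done by the time of sending: (M − 7) − 14 = M − 21
- Days on which session 2 is allowed after sending: M − (M − 7) = 7

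| M | Packet sent | Latest session 2 | Overlap | Session 1 cut-off | Latest session 1 | Window closes |
|---|---|---|---|---|---|---|
| 28 | day 21 | day 28 | 7 days | day 7 | day 14 | day 35 |
| 30 | day 23 | day 30 | 7 days | day 9 | day 16 | day 37 |
| 31 | day 24 | day 31 | 7 days | day 10 | day 17 | day 38 |

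The overlap is 7 days however a month is counted. With M = 30, a session 1 on days 10 to 16 puts session 2 on days 24 to 30, after the packet has gone out.

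**Illustration of size only.** Suppose session 1 were equally likely on each permitted day.
- Counting whole days 0 to 16 with M = 30: 7 of 17 = 41%.
- Treating time as continuous over M − 14 days: 7/16 = 44% for M = 30, 7/14 = 50% for M = 28 and 7/17 = 41% for M = 31.
- If session 1 never falls before day 3 (M = 30): 7 of 14 = 50%.

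These are shares of packets sent before session 2. They are not shares of packets answered before it.

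**Room in the existing window.** A session 2 on day 30 leaves 37 − 30 = 7 days before the window closes.

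**The case against.** The best reply is that sending is not collecting. The window stays open to about day 37 and staff keep following up, so some women sent the packet on day 23 will answer after session 2. That stands. A reader might infer from the illustration that 41% to 50% of CSQ ratings will describe half the program. The documents do not support that: they give no distribution of session dates, the percentages rest on a uniform assumption, and they count packets sent. Scheduling starts directly after baseline, and a session 1 by about day 9 removes the problem. A gap shorter than 14 days reduces it.

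A reader might also infer that the one-month results for Aim 2 fail as a whole. That goes too far. Those comparisons are anchored to baseline by design, the mixed models use all three time points, and the 3-month assessment repeats AET initiation and every scale except the CSQ, well after the session period.

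Two further replies carry some weight. Attendance is met by one of the two sessions, so some ratings after a single session are built into the design. The optional interviews after the intervention also give feedback on acceptability. Neither answers the point for a woman who attends both sessions but rates the program between them.

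Finally, the participant road map (Appendices 9.23 and 9.24) is a figure that was not available, so a timing rule there cannot be excluded.

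**Conclusion.** The point holds as a conflict between stated rules. Followed as written, they allow the only CSQ, and the other one-month measures, to be completed before session 2. The overlap is 7 days under any definition of a month. With a 14-day gap it affects women whose session 1 falls after about day 9 (day 7 to day 10 for months of 28 to 31 days). The main consequence is for the acceptability criterion. A lesser one is that some baseline to one-month changes can be mid-intervention. The number of women affected cannot be derived from the documents, and the 3-month assessment is untouched. The conclusion assumes that no rule in the missing road map holds the packet back. The change is worth making because it is nearly free and early CSQ ratings cannot be replaced.

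**What to change.** Keep the window of 7 days either side. Amend Section 5.4 so that the CSQ, and preferably the rest of the 1-month packet, is released only once session 2 is complete, or at day 30 if session 2 has not taken place. If the sponsor does not want the timing of the other outcomes to depend on attendance, holding the CSQ alone protects the primary criterion.

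Use the session date already recorded in the interventionist post-session survey (Appendix 9.26), together with the packet completion date, to flag any response given before session 2. State in Section 7.5 that the CSQ result will be reported with and without flagged responses.

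Do not move the window to start at day 30 and run to about day 44, although that may look like the natural remedy. It would delay every packet by at least 7 days. It would also blur the estimate of initiation within one month of baseline, because the AET item asks about current use and would pick up later starts.

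Cost: a short amendment and a change to the release trigger. Some packets or CSQs go out up to about 7 days later, with less time for reminders; a session 2 on day 30 leaves until about day 37.

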5.5 Description of Study Process

After completing the baseline assessment and enrollment, we will schedule the patient's intervention sessions. Sessions will take place via videoconferencing software (Zoom). If a patient prefers, these sessions can also be held in person or over the phone. Each session will last approximately 60 minutes. Participants will be reminded that they can decline to discuss any topic that is presented during the sessions. Interventionists will complete a post-session survey following each session (Appendix 9.26). 80% of sessions will be audio-recorded and at least 10% randomly selected, stratified by interventionist, and reviewed with study staff for treatment fidelity. Content fidelity will be assessed by calculating the percentage of key intervention topics addressed out of total topics, with a goal of 90%. Feedback will be given to interventionists to enhance adherence to the protocol.

The nurse-led intervention will be administered by trained study staff (under direct supervision and guidance from the PI) and study sessions will be conducted in English or Spanish using an intervention manual. This manual will be finalized after the completion of Phase I of this study with input from [name], [name], and [name]. Following the intervention, we will offer participants optional semi-structured interviews to gather feedback on the sessions (Appendix 9.27). We will then modify the intervention iteratively to reflect participants' feedback in order to best address the needs of patients who have not started or are hesitant to initiate their AET medication. The study materials, including consent forms, recruitment materials, patient-facing materials and study measures, not otherwise available in Spanish from their licensor, will be translated (forwards and backwards) into Spanish by Linguistic Systems, Inc and Spanish-speaking investigators and coordinators in our Cancer Outcomes Research and Education Program (CORE). This group has extensive experience providing translation services for researchers at Harvard Medical School and Beth Israel Deaconess Medical Center. After the translation, a second linguist will edit the Spanish-language materials for quality assurance, following best practices in the translation industry.

Special Concerns

We do not anticipate any major complications with this study. To reduce burden, participants will be offered the opportunity to complete the intervention sessions via Partners approved videoconferencing software (Zoom). If a patient prefers, these sessions can also be held in person or over the phone. If a participant expresses distress during the study sessions, they will be reassured that they can stop the session and they are not required to respond to any topics presented during the sessions which they find upsetting. They will also be reminded that study participation is voluntary. If a participant remains distressed, the principal investigator, a psychologist, will offer a referral to supportive care services in the Psychiatric Oncology Service in the MGH Cancer Center, and assess safety prior to terminating the intervention session.

Participants may experience some discomfort talking about some of the topics brought up during the sessions or answering study assessment questions; however, they may choose not to discuss topics or answer questions that are distressing. Participants may also experience some discomfort being audio recorded, for the purposes of qualitative data collection. Confidentiality will be detailed on the consent form and discussed in detail so that participants are fully informed of their right to request information and to withdraw from the study at any time without impacting their care. We will also discuss the importance of maintaining confidentiality at the beginning of each session.

Breach of confidentiality is a concern in all studies with human subjects. Patient participants will be completing individual intervention sessions that will be audio-recorded; thus, safeguards will be put in place to ensure that participant information is kept private and confidential. Participants' data will be kept on Lab Archives, a Mass General Brigham electronic secure research lab notebook, and Business Dropbox, a cloud-based storage that is compliant with Mass General Brigham's policies and procedures. Data stored on Lab Archives and Dropbox

will only be accessible to the Principal Investigator and IRB-approved study staff. Data will not be shared with individuals other than study staff and any identifiable information about study participants will be destroyed after all data analyses are complete.

Compensation

Participants will not endure any additional costs as part of their participation in this research study. As such, we do not anticipate any financial burden on study participants. The study intervention visits will not be billed.

We will remunerate participants \$10 for each assessment packet completed for up to \$30 total.

Handling of Study Documents

Study source documents, including but not limited to signed informed consent forms, completed eligibility checklists, and participant questionnaires, will be scanned and stored digitally as certified copies on a secure drive only available for access to trained study staff working with the documents. The drive will be only accessible with proper invitation to the drive by the Principal Investigator through their Partners account, which will require personal username and password information to access. Trained study staff will follow specific standard operating procedures for handling source documents and certifying each copy appropriately. The procedures are as follows. After source documentation is filled out by the participant, study staff will collect the original source document. The study staff member scanning documents will be kept as consistent as possible throughout the duration of the study to ensure uniformity among source documentation handling. Location, time, and date of the scanning of the document will be recorded at the time of scanning. Study staff will fill out the Source Documentation Certified Copy Cover Sheet (Appendix 9.29) and include this as the first page of the electronic version of the source document. After the source document is scanned and the corresponding electronic document is confirmed to be legible, all facing the correct direction, and together as a single document, it will be collected and destroyed immediately. Study staff will destroy the original copy of the source document by following MGH procedures of destroying documents with Personal Health Information (PHI). Electronic versions of source documents will allow study staff to access these documents regardless of where the original copy is stored, which may be inconvenient, increase study staff burden, and study cost if storage of documents is far from the location where research activities will be conducted or required to be placed in long term storage. This process has been developed streamlined, and successfully implemented in DF/HCC Protocol #18-603.

5.6 Adverse Reactions and Their Management

Reporting Adverse of Unanticipated Events

We do not anticipate any harm with our study procedures. While some topics probed in study assessments and the intervention may be sensitive in nature, our study staff has extensive experience conducting social behavioral intervention on sensitive topics without any adverse events. No adverse or unanticipated events occurred in previous studies of psychological interventions conducted by our research group. Reportable adverse events would include a breach of confidentiality. Should adverse or unanticipated events occur during the study, a trained study staff member will report the events to the IRB as soon as they are discovered.

Anticipated Reactions

As Phase 2 of this study consists of a 2-session, in-person or virtual intervention with 3 study surveys, there are no ingested medications and no biomedical procedures. It is unlikely that participants will be at any risk for physical harm because of study participation. Participants may find some of the questions to be emotionally upsetting, and if so, they may experience some distress.

Reaction Management

A detailed consent form will be signed by study staff after the participant provides consent, following the explanation by study staff. The consent form will include all study procedures, information about potential risks and benefits of participation, and information regarding whom the participant can contact for further questions. It will also state that participation is voluntary, that participants can refuse to answer any questions, that they can withdraw from the study at any time, and that study participation is in no way related to their medical care. All study staff will complete the required human subjects training before they can work on any human subject aspects of the study.

If a participant expresses distress during the psychological intervention visits, they will be reassured by the clinician or study staff member conducting the intervention session that they can stop at any time and that they do not need to continue participating in content or discuss any intervention topics/questions which they find upsetting. They will also be reminded that study participation is voluntary. If participants remain distressed, they will be offered an opportunity to meet with a psychologist in the Psychiatric Oncology Service at the MGH Cancer Center to help address their distress.

For all participant assessments given throughout the study, study staff will review assessments upon receipt from participants for completion and to assess distress. On the HADS, patients who endorse ≥ 11 on even items for a more severe range for depression will be called by qualified study staff (e.g., [name], a licensed clinical psychologist, as well as trained clinical psychology practicum fellows). If a participant completes the distress assessment online through the secure REDCap portal, a study staff member will check the responses and notify the PI for follow-up if needed within 72 hours of receipt. If a participant completes assessments on paper, study staff will check the responses and notify the PI for follow-up if needed within 72 hours of receipt. If a participant completes assessments over the phone, study staff will notify the PI for follow-up if needed within 72 hours of receipt. If the patient needs further outpatient services for depression, including pharmacotherapy, or is at risk for self-harm requiring hospitalization, study staff will make the necessary referrals for treatment. For example, for patients who are distressed but in no danger to self or others, study staff will refer either to the MGH Oncology Social Work Service or to the MGH Outpatient Psychiatry Department [contact]), including the Cognitive-Behavioral Therapy Program. If suicidality or risk of harm to others is otherwise discovered at any study visit, the participant will be referred to appropriate services. Specifically, in the case that hospitalization is required, study staff will contact and escort the patient to the MGH Acute Psychiatry Service [contact]), with the aid of the MGH Police & Security if necessary [contact]). If a referral for outpatient services is made, or the patient requires escort to the MGH Acute Psychiatry Service, study staff will notify the health care team, including the primary oncologist.

The PI and trained study staff will meet weekly to review study progress, ensure proper implementation of the intervention, and review any adverse reactions that occur. The PI and the research assistant will review consents and collected data to ensure proper adherence to study protocol.

